5.4 Inclusion/Exclusion Criteria

Inclusion criteria: All participants (both GW and non-GW Veterans) must meet criteria for CMI, defined as self-report of at least two of the following 1) fatigue that limits usual activity; 2) musculoskeletal pain involving two or more regions of the body; 3) cognitive symptoms (memory, concentration, or mood disturbances).¹³ GW Veterans must have been deployed to the GW theater of operations between 8/1990 – 8/1991,

have symptoms of CMI that began after 8/1990, lasted at least 6 months, and are present at the time of the interview.

Exclusion criteria: At baseline, the MINI psychiatric interview⁷⁵ will determine psychiatric exclusion criteria: 1) current psychotic disorder; 2) current bipolar affective disorder with mania; 3) current suicidal or homicidal ideation. Additional exclusion criteria include a chart diagnosis of borderline or antisocial personality disorder or prior *formal* participation in MBSR or CDSMP. We will include subjects with the entire range of alcohol SUD (defined by the MINI), but exclude those for whom alcohol use poses a safety threat (defined as current drinking and a past-year history of alcohol-related seizures or delirium tremens). We will also exclude current DSM-V substance use disorder other than cannabis or nicotine, as well as inpatient psychiatric admission within the past month. Medication, supportive individual or group counseling, case management, and self-help programs will be allowed and assessed as potential covariates. As of July 2020, participants must have the required technology in order to participate in VVC intervention groups.

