Quantitative data will be analyzed following the completion of the final assessments of the last subject cohort, which is projected to take place in the last six months of Year Four of the study. The dataset will be analyzed by [name], in consultation with [name].

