6.0 Reporting

When an unexpected serious adverse event occurs, we will log it in an “Adverse Events & Problems” log, to be used for providing reports to the Data Safety Monitoring Board (DSMB), in addition to submitting a report to the IRB within 5 days as required. All other adverse events, problems, and protocol deviations will be logged and reported to the Safety Monitor and the IRB with annual reviews.

Adverse Events related to worsening depression symptoms will be actively monitored by tracking PHQ-9 scores. We will define as an AE an increase in PHQ-9 depression score by 2 or more severity categories. For example, if a patient experiences an increase in depression from moderate to severe, this would be an increase in two categories of severity. The PHQ-9 categorizes depression as none, mild, moderate, moderately severe, and severe according to the total score; this has been previously validated. At the midpoint of the study, the data monitor would then analyze whether significantly greater adverse events occur in one arm of the study, which might warrant stopping the study.

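### Measured from baseline, the PHQ-9 adverse-event rule cannot be met by participants who start moderately severe or severe, so the depression component of the mid-study safety comparison loses sensitivity by an amount the documents do not allow to be sized

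*Combined protocol and SAP*

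**What the plan says.** Section 6.0 (Reporting) sets out how worsening depression is watched: "Adverse Events related to worsening depression symptoms will be actively monitored by tracking PHQ-9 scores". The event is then defined: "We will define as an AE an increase in PHQ-9 depression score by 2 or more severity categories". The scale is given as well: "The PHQ-9 categorizes depression as none, mild, moderate, moderately severe, and severe according to the total score". The section's worked example is a move from moderate to severe, which it counts as two categories. It does not name the score against which the rise is measured (baseline, previous visit or lowest score).

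The count feeds a safety look halfway through the study, at which "the data monitor would then analyze whether significantly greater adverse events occur in one arm of the study"; the section adds that a difference might justify stopping. No test, significance level or boundary is given, and the midpoint of the study is not defined. Other events are also recorded: "All other adverse events, problems, and protocol deviations will be logged and reported to the Safety Monitor".

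The table in section 5.5 schedules the PHQ-9 at baseline, post-treatment, 3 months and 6 months, as a secondary outcome. Section 5.4 lists the psychiatric exclusions determined by interview as "1) current psychotic disorder; 2) current bipolar affective disorder with mania; 3) current suicidal or homicidal ideation", and separately excludes "inpatient psychiatric admission within the past month". None of these is a limit on depression severity, and mood disturbance is one of the symptoms that count toward the definition of CMI.

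**The concern.** A rule that needs a rise of two steps on a five-step scale has a ceiling: anyone who starts within one step of the top has no room to meet it. Such participants can be enrolled, because nothing in section 5.4 screens on PHQ-9 score. Section 5.1 itself names the possibility that either programme could be stressful and worsen symptoms.

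What is at stake is a safety comparison that might stop the study. Its only systematic measure of worsening depression cannot count anyone from the most depressed starting groups. For them the comparison depends on events that someone happens to report or notice.

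**Working it through.** **1. The plan's own example.** Code the categories none = 0, mild = 1, moderate = 2, moderately severe = 3, severe = 4. Moderate to severe is 4 − 2 = 2 categories, which agrees with section 6.0.

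**2. Largest possible rise from each start.** This is 4 minus the starting code, compared with the threshold of 2.

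| Starting category | Largest rise | Can meet the rule? |
|---|---|---|
| None | 4 | Yes |
| Mild | 3 | Yes |
| Moderate | 2 | Yes |
| Moderately severe | 1 | No |
| Severe | 0 | No |

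The plan's example thus uses the highest start that can still qualify. Of the 4 + 3 + 2 + 1 = 10 possible upward moves, 6 count as an event: 3 from none, 2 from mild and 1 from moderate.

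**3. Does the comparator matter?** Partly. Against the previous or the lowest score, a high starter who first improved to moderate or better could later qualify. A participant who never falls below moderately severe cannot qualify under any comparator.

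**4. Illustration of the loss.** Let s be the share starting in the top two categories. Assume worsening that ought to be counted is equally common at every starting level, and that the rule catches all of it among the other starters. Then in each arm

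registered rate = (1 − s) × true rate.

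The assumptions, none of them in the documents, are:
- true rates of 5% and 20%;
- the values of s;
- a two-sided Fisher exact test at 5%, applied to PHQ-9 events alone;
- the number per arm with a follow-up score. I use 77, which is half of the planned 308 split over two arms (308 / 2 / 2 = 77), and 50 to allow for fewer scores being available.

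Power by full enumeration of both binomial distributions:

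| s | Registered rates | Expected events, 77 per arm | Power, 77 per arm | Power, 50 per arm |
|---|---|---|---|---|
| 0 | 5% vs 20% | 3.9 vs 15.4 | 0.77 | 0.51 |
| 10% | 4.5% vs 18% | 3.5 vs 13.9 | 0.71 | 0.44 |
| 20% | 4% vs 16% | 3.1 vs 12.3 | 0.64 | 0.37 |
| 40% | 3% vs 12% | 2.3 vs 9.2 | 0.46 | 0.23 |

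The level of power depends heavily on the assumed number per arm: with 50 it is about one half even without a ceiling. The direction does not depend on it.

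**The case against.** The strongest reply is that the ceiling affects one ingredient of a wider comparison. Section 6.0 has the monitor compare adverse events, not PHQ-9 events alone, and all other events are logged. A reader might infer from the table that the whole mid-study comparison loses that much power. The documents do not support this: they describe no separate PHQ-9 test, and the mix of other events is unknown.

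A reader might also infer that high starters go unmonitored. They do not. The risk procedures in section 5.1 cover distress, worsening and suicidality for each participant, and PHQ-9 totals are collected from everyone. What stands is that those procedures act on individuals and depend on reporting, and no passage gives a depression criterion for high starters to replace the category rule.

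A third tempting inference is bias between arms. Randomisation balances the share of high starters on average, so the effect is dilution.

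Two further replies limit the size of the point. The exclusions for suicidal ideation and recent psychiatric admission may reduce the share starting in the top categories. And the dilution model treats countable worsening as equally common near the top of a bounded scale. If it is rarer there, the loss is smaller than s; if commoner, larger. Both are fair, and both are reasons for not putting a figure on the loss.

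**Conclusion.** The point holds as a limit on sensitivity. Against baseline, two of the five starting categories can never produce the event; this follows from section 6.0 alone. That such participants can be enrolled follows from section 5.4. The PHQ-9 component of the mid-study comparison is therefore less able to show a real difference between arms than section 6.0 implies.

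The size cannot be derived, because the documents give no baseline PHQ-9 distribution, worsening rates, definition of the midpoint or test. The falls in power shown above (0.77 to 0.64 or 0.46 with 77 per arm; 0.51 to 0.37 or 0.23 with 50) are illustrations under stated assumptions. They apply to the PHQ-9 component only. The primary efficacy analysis is not affected. This should be corrected, but it does not undermine the trial.

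**What to change.** Keep the category rule and add to section 6.0:

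1. At the mid-study look, the safety monitor alone also receives PHQ-9 change from baseline by arm, among those with a follow-up score, and category-rule events by baseline category and arm. If that look has already taken place, which is possible with Version 10 of a running study, give the same table with the next safety report. This step does most of the work, because change scores can show worsening that the rule cannot count.
2. State which score the rule is measured against. Naming baseline would remove the ambiguity but not the ceiling.
3. Have the study clinicians and the monitor state how worsening is counted for participants who start in the top two categories. No cut-off is proposed here.
4. Add a sentence saying that the table is a safety summary, separate from the main analysis. Section 5.6 says: "Quantitative data will be analyzed following the completion of the final assessments of the last subject cohort".

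The cost is a short addition to the text, some clinician and monitor time, and one table from totals already scheduled at baseline, post-treatment, 3 and 6 months, with no added burden on participants. The downside is an interim look by arm at a secondary outcome, which must stay with the monitor and be kept from the investigators.

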7.0 Privacy and Confidentiality

The study will obtain Protected Health Information by collecting data (e.g. medications and other treatment relevant to the symptoms evaluated for the study) from the subjects’ CPRS records, as well as contact information (PII) for following up with subjects regarding ongoing study procedures. Health information will also be collected through the questionnaires and interviews. This health information will be maintained as de-identified study data, and will not be disclosed to unauthorized entities. We will be obtaining a Certificate of Confidentiality for this study, as we ask about substance use.

A password-protected crosswalk will be maintained to link identifying information (full names and last 4 SSN) to study subjects’ unique study IDs (e.g. 695-001, 695-002, 695-003....695-308). All files containing study data, hard copy or electronic, will include only the subject’s study ID so that no data can be linked directly to an individual. All study team members, as VA employees (WOC or otherwise) are required to undergo Privacy & HIPAA training as well as VA Privacy and Information Security Awareness and Rules of Behavior. Any non-VA-affiliated study team members will be required to undergo equivalent training. Only study team members will have access to the electronic study

folder, located on the R: drive on the VA server. Hard copy data and consent forms will be stored in locked filing cabinets in the offices of the PI and/or the Project Manager.

8.0 Communication Plan

N/A, this is not a multi-site research project.

9.0 Information Security and Privacy

Data pertaining to medication usage and other treatment received during the subject's study enrollment period will be gathered from accessing CPRS and recording the information on a hard copy paper, linked to the participant by Study ID only, which will be filed in a locked researcher file cabinet (in the office of the Project Manager or the PI). Consent forms and other hard copy documents with identifying information (e.g. emergency contact page) will be filed in separate hanging folders from any documents with study IDs and study data on them, so that the identifying information cannot be linked to the corresponding data.

Data from self-report measures will be collected through an MS Access database. The administering researcher will open the database from the study folder on a VA computer, and then the participants will fill out the questionnaires. Each set of questionnaires will be linked to subjects through their study IDs or other unique identifiers (no PII recorded in the MS Access database), and these identifiers will be recorded and tracked by the study team. When needed, a report or query of these outcome/response data from these questionnaires will be generated from MS Access and saved to the study folder.

Audio files from the qualitative interviews will be available to certified medical transcriptionists through secure VA folders; all transcriptionists are VA employees. Additionally, the interviewer does not use the name of the subject during the interviews to help maintain confidentiality.

Participants in VVC interventions will be notified about the limits to confidentiality inherent in an internet delivered group format at the time of their consenting.

